2.2 Secondary Objectives

1. To determine the operative time of the Whipple procedure when performed using the Thunderbeat™ device. This will be compared to patients whose Whipple procedure will be performed using conventional dissection and hemostasis techniques. Will this device reduce the amount of time spent in the operating room for both the patient and the surgeon?
2. To determine the cost of using the Thunderbeat™ device during the Whipple procedure. This will be compared to patients whose Whipple procedure will be performed using conventional dissection and hemostasis techniques. Will the use of this device be fiscally feasible?

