9.0 STATISTICAL CONSIDERATIONS

9.1 Study Objectives and Endpoints

The primary objective of the study is to determine if the use of the Thunderbeat™ device provides a reduction in operative blood loss. The measurement of operative blood loss will come from the intraoperative anesthesia notes where estimated blood loss is recorded during each surgical procedure.

The secondary objectives are intraoperative and postoperative morbidity, hospital length of stay and operative time.

Primary endpoint

The primary endpoint will be the estimated operative blood loss. The estimated blood loss will be measured per the standard of care and will be documented in the operation log.

Secondary endpoints

- Operation time measured from the beginning of the surgical procedure (incision of the skin) to the end of the surgical procedure (closure of the skin).
- Anesthesia time measured from the initiation of anesthesia induction to the time of extubation
- Perioperative complications:
 - Iatrogenic injury
 - Need for conversion from laparoscopic approach to open procedure
 - Need for the use of other hemostatic devices or therapies
 - Intraoperative requirement of blood product transfusion
- Postoperative complications through 90 days from day of surgery:
 - Secondary bleeding/hematoma
 - Wound infection
 - Gastroparesis
 - Postoperative pancreatic fistula
 - Intraabdominal abscess

- Anastomotic leakage
- Re-intervention (operational)
- Postop requirement for blood product transfusion
- Hospital mortality
- Overall cost of the operation, calculated by the indirect and direct costs during the hospital stay and the costs accumulated 90 days postoperatively

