9.4 Data Analysis

Data analysis for this study will be descriptive in nature. Demographic and clinical characteristics of the sample, as well as intraoperative findings and post-surgery complications will be summarized using descriptive statistics. The incidences of surgical complications and procedure-related adverse events will be calculated, and the confidence intervals will also be provided.

Patients assigned to the Thunderbeat™ group will be compared with those who had conventional techniques using χ^2 tests for categorical variables and Student's t-tests for continuous variables. For the t-tests equal variances were not be assumed, unless significant by Levene's test. Mann-Whitney *U* tests will be utilized for non-normally distributed variables. Two-tailed *P* values 0.05 will be considered statistically significant.

Multivariate analyses for intraoperative blood loss (mL), operative time (minutes), postoperative morbidity (any grades 1–5 and major grades 3–5), and hospital length of stay (days) will be performed using binary logistic regression and linear regression models to examine the relationship between intervention groups and examined outcomes and to identify potential confounders. The results of multivariate analyses will be expressed as odds ratios with corresponding 95% confidence intervals. All analyses will be performed using SPSS 20.0 statistical software (SPSS Inc.Chicago, IL).

REFERENCES

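### Section 9.4 would probably give 90-day cost a rank test with no monetary estimate, which cannot answer the fiscal-feasibility question in Section 2.2

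*Combined protocol and SAP*

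**What the plan says.** - **Objective.** Section 2.2 lists as its second aim "To determine the cost of using the Thunderbeat™ device during the Whipple procedure", to be compared with conventional technique, and then asks: "Will the use of this device be fiscally feasible".
- **Endpoint.** Section 9.1 lists among the secondary endpoints "Overall cost of the operation, calculated by the indirect and direct costs during the hospital stay and the costs accumulated 90 days postoperatively".
- **Analysis.** Section 9.4 compares the groups with "Student's t-tests for continuous variables" and adds that Mann-Whitney U "tests will be utilized for non-normally distributed variables". It makes no exception for cost and gives no criterion for judging non-normality.
- **What is not there.** The Section 9.4 regression models cover blood loss, operative time, morbidity and length of stay, but not cost. The descriptive sentence names demographic and clinical characteristics, "as well as intraoperative findings and post-surgery complications will be summarized using descriptive statistics"; it does not name cost. Confidence intervals are promised for complication and adverse-event incidences and for the regression results. No mean cost difference or interval for it is planned.

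**The concern.** The cost endpoint runs to 90 days and takes in whatever follows from fistula, abscess, anastomotic leak, re-operation and transfusion, all listed in Section 9.1. Totals of this kind usually have a long right tail, because a few complicated stays cost several times the typical one. A reader applying Section 9.4 to such data would turn to Mann-Whitney.

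Mann-Whitney asks whether a value from one arm tends to exceed a value from the other. It uses the rank of an expensive stay and not its size, and as planned it returns a p-value and no amount of money. A hospital deciding whether it can afford the device needs the amount. At stake is a stated secondary objective that could end with a significance statement and no usable answer. In some cost patterns that statement could also lean away from the difference in means.

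**Working it through.** The plan states no figure for cost, so there is none to reproduce. **Every cost input below is an assumption chosen to show the mechanism. The documents give no cost, price or cost distribution.** From the documents come only 30 patients per arm (Section 9.3) and two-sided testing at 0.05 (Section 9.4).

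**1. Ranks and means can disagree: a fixed data set, 30 v 30.**
- Device: 25 patients evenly spaced from 90 to 102 (mean 96) and 5 at 400. Mean = (25 × 96 + 5 × 400)/30 = 4,400/30 = 146.7.
- Conventional: 28 evenly spaced from 100 to 113.5 (mean 106.75) and 2 at 300. Mean = (28 × 106.75 + 2 × 300)/30 = 3,589/30 = 119.6.
- Medians are 97.25 v 107.25. Mann-Whitney U = 162.5, p = 0.00002, in favour of the device being cheaper.
- The mean difference is +27.0 per patient, so the device is dearer in this sample (Welch p = 0.24).

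**2. How a reversal arises.** Assume a base cost of 25,000 (SD 5,000), a complicated stay that adds 50,000 on average, complication rates of 20% conventional v 10% device, and a device that adds *a* to each case.
- Mean difference = *a* − (0.20 − 0.10) × 50,000 = *a* − 5,000. This is −2,000 at *a* = 3,000 and −4,500 at *a* = 500. The device is cheaper on average in both.
- For the ranks, treat every complicated stay as dearer than every uncomplicated one (an approximation). Then P(device dearer) ≈ 0.8 × 0.9 × Φ(*a*/7,071) + 0.8 × 0.1 + ½ × 0.2 × 0.1, where 7,071 = 5,000√2.
- At *a* = 3,000: 0.72 × 0.664 + 0.08 + 0.01 = 0.57. This is above 0.5, so ranks lean the wrong way.
- At *a* = 500: 0.72 × 0.528 + 0.09 = 0.47. This is below 0.5, so ranks lean the right way.

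**3. How often, by simulation (30 per arm, lognormal complication cost).**

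| Scenario | Mann-Whitney leans to device dearer | Significant in that wrong direction |
|---|---|---|
| 20% v 10%, *a* = 3,000 | about 83% | about 16% |
| 20% v 10%, *a* = 500 | about 35% | about 1% |
| 40% v 30%, *a* = 1,000 | not tabulated | about 1% |

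In the first scenario the rank and mean directions disagree in 46–50% of trials. That needs a baseline: with no true difference (20% v 20%, *a* = 0) they still disagree in about 25%. Disagreement in sign is therefore largely noise at this sample size.

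**4. When there is no reversal.** With lognormal costs of equal log-SD 0.6 and a device mean 10% lower, P(device cheaper) = 0.55. Ranks and means then agree in the population.

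**5. Would the rule be triggered?** In the independent scenarios examined, which used skewed lognormal and mixture costs, Shapiro-Wilk rejected normality in at least one arm in 98–100% of trials. The plan does not say that Shapiro-Wilk will be used.

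**6. What the mean difference can deliver.** Take step 2 with *a* = 3,000, and let *v* be the CV of the complication cost. Per-arm variance = 5,000² + p × 50,000² × (1 + *v*²) − (p × 50,000)².
- *v* = 0.5: 550.0 million (conventional) and 312.5 million (device). SE = √(862.5 million/30) = about 5,400.
- *v* = 1.0: 925 million and 500 million. SE = √(1,425 million/30) = about 6,900.
- The 95% half-width is then roughly 1.96 × 5,400 to 1.96 × 6,900, or about 10,600 to 13,500, around a true −2,000. The sample mean difference itself has the wrong sign in about 35–39% of trials.

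**The case against.** The strongest reply is that the plan commits to nothing wrong. Section 9.4 describes the analysis as descriptive, Section 2.2 asks for the cost to be determined, and a Mann-Whitney p-value does not stop anyone reporting arm means. The t-test is the default, so the move to Mann-Whitney is likely rather than fixed. This is one secondary endpoint of a feasibility study with no power claim for cost, and step 6 shows that the mean difference will be imprecise too.

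Much of that stands. A reader might infer that the planned test will answer the cost question in the wrong direction. The documents do not support this. A reversal needs arms that differ in shape, and the large rates in step 3 rest on an assumed 3,000 added to each device case. No device cost is given. Section 1.2 describes conventional dissection as slow and heavy on ligatures, clips and sutures, so the net per-case cost could be small or even negative. It would be equally unsupported to state as fact that cost will be skewed.

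The reply does not remove the gap. Freedom to report means is not a plan to do so, and cost is absent from the items to be summarised. If the rule is triggered, the only specified comparison of cost is a rank test. Even where ranks and means agree, that test gives no monetary figure. An imprecise estimate of the right quantity, shown with its interval, is more useful for a budget than a p-value about another quantity.

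**Conclusion.** The point holds in a limited form. Section 9.4 makes no exception for cost in its Mann-Whitney rule and plans neither a mean cost difference nor an interval. If 90-day cost is right-skewed, which is likely but not shown, the specified analysis cannot answer the question in Section 2.2. That conclusion rests on reading fiscal feasibility as a matter of mean cost per patient, and it needs no assumed cost figures.

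Opposite directions are a possibility and not a prediction. Wrong-direction significance ranged from about 1% to about 16% in the step 3 scenarios, driven by the assumed costs, and should not be quoted as a property of this trial. The change is worth making because it costs almost nothing, but it affects one secondary endpoint and leaves the primary analysis untouched.

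**What to change.** Add a sentence to Section 9.4: overall 90-day cost will be compared as the difference in arithmetic mean cost per patient between randomised arms, with a 95% confidence interval (bootstrap or Welch), whatever the distribution. Medians and quartiles may be given as description, and Mann-Whitney is supportive at most. State which interval is primary; with only a handful of costly stays per arm, either may have imperfect coverage.

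The cost is one sentence and a few lines of programming. Sample size, data collection and patient care do not change. The drawback is that with 30 per arm the interval will be wide and probably will not settle whether the device saves or costs money. The report should say this and should not read a non-significant difference as evidence of equal cost.

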3.0 PATIENTSELECTION

3.1 Inclusion Criteria

1. Scheduled to undergo an elective open or laparoscopic Whipple procedure
2. At least 18 years of age.
3. Karnofsky performance status \geq 80% (see Appendix A).
4. Able to understand and willing to sign a written informed consent document.

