9.3 Sample Size

Appropriate sample size is calculated based on assumption of difference of 20 percent in blood loss in favor of the Thunderbeat™ device as compared with conventional techniques. This difference is considered clinically relevant based on previous similar studies [9-11]. A sample size of 60 is considered sufficient to prove this difference, if present (alpha error set at 0.05, power>80 percent).

Approximately 100 patients per year undergo a Whipple procedure at Washington University Medical Center. The estimated time frame to enroll 60 patients is approximately 18 to 24 months.

The total expected enrollment is 60 patients: 30 Thunderbeat and 30 conventional.

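### Section 9.3 sizes the trial on a 20 percent difference in blood loss, but no blood-loss analysis in 9.4 commits to estimating that reduction with a confidence interval

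*Combined protocol and SAP*

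**What the plan says.** All references are to the combined protocol and SAP.

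- **Sizing (9.3).** "Appropriate sample size is calculated based on assumption of difference of 20 percent in blood loss in favor of the Thunderbeat™ device". The section adds "A sample size of 60 is considered sufficient to prove this difference, if present", with "alpha error set at 0.05, power>80 percent". It gives no control mean, SD, CV or mL equivalent of the 20 percent.
- **Primary endpoint (9.1).** Estimated operative blood loss, with no effect measure named. Appendix B records it as a volume in cc.
- **Two-group tests (9.4).** Student's t-tests for continuous variables, except that Mann-Whitney U "tests will be utilized for non-normally distributed variables". Significance: "Two-tailed *P* values 0.05 will be considered statistically significant".
- **Regression (9.4).** "Multivariate analyses for intraoperative blood loss (mL), operative time (minutes" and further outcomes are to be analysed by logistic and linear regression. The outcomes are not matched to model types, and the results are all to be given as odds ratios with 95% confidence intervals.
- **Other intervals (9.4).** Promised only for the incidences of complications and adverse events.
- **Population (3.1).** "Scheduled to undergo an elective open or laparoscopic Whipple procedure", so open and laparoscopic cases are compared together.

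**The concern.** The trial is sized on a proportional effect, and its report should say how large the proportional reduction was and which reductions the data allow. Followed as written, 9.4 need not produce that. The t-test compares means in mL. Mann-Whitney, as planned, yields a P value. The regression on mL is to be summarised by a quantity that a linear model does not produce.

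The trial could therefore end with a P value for its primary endpoint and no statement of whether 20 percent, a smaller reduction, or none is compatible with the data. This matters more because 9.4 calls the analysis descriptive and 2.1 calls the study a feasibility/QI registry trial. In such a study the estimate and its precision are the main product.

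**Working it through.** **1. The plan's own figure.** N = 60 can be neither confirmed nor refuted, because no SD or CV is given. Solving backwards for 30 per arm, two-sided alpha 0.05 and 80% power (normal approximation):

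- detectable standardised difference = (1.960 + 0.842) × √(2/30) = 0.723
- largest CV compatible with a 20 percent reduction on the raw scale = 0.20 / 0.723 = 0.28

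The missing CV is a separate matter. It does show that 9.3 treats the 20 percent as a fraction of the control value. Read instead as 20 percentage points between two proportions, it would need a total of 124 to 194 for control rates of 30% to 60%, not 60.

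**2. What each planned blood-loss analysis delivers.**

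| Analysis in 9.4 | Quantity | CI promised for blood loss? | Gives a percent reduction? |
|---|---|---|---|
| t-test | difference in raw means | no | no |
| Mann-Whitney U | P value | no | no |
| Linear regression on mL | coefficient in mL, but to be reported as an odds ratio | only for an odds ratio, which this model does not produce | no |
| Logistic regression, if blood loss were dichotomised (no cut-point given) | odds ratio | yes | no |

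Software may print a CI for the mL difference. Turning that into a CI for a percentage must also allow for uncertainty in the control mean, and 9.4 does not provide for this.

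**3. The interval that is missing.** Assume lognormal blood loss with the same CV in both arms; the documents give no distribution.

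- log-scale SD: s = √ln(1 + CV²)
- 95% CI for an observed ratio of 0.80: 0.80 × exp(± t × s × √(2/30)), with t(0.975; 58 df) = 2.002

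| Assumed CV | s | Half-width (log) | 95% CI |
|---|---|---|---|
| 0.3 | 0.294 | 0.152 | 0.69 to 0.93 |
| 0.5 | 0.472 | 0.244 | 0.63 to 1.02 |
| 0.7 | 0.631 | 0.326 | 0.58 to 1.11 |
| 1.0 | 0.833 | 0.430 | 0.52 to 1.23 |

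From a CV of 0.5 upwards, an observed 20 percent reduction would be compatible both with no effect and with a reduction of more than a third.

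**4. Does the scale cost power?** Simulated lognormal data, 30 per arm, two-sided 0.05. The first three rows are from 10,000 trials per setting:

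| True reduction, assumed CV | Welch t, raw | Mann-Whitney | t on logs |
|---|---|---|---|
| 20%, CV 0.3 | 80% | 80% | 82% |
| 20%, CV 0.5 | 40% | 41% | 44% |
| 20%, CV 0.8 | 19% | 21% | 23% |
| 40%, CV 1.0 | 51% | 61% | 64% |

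The plan switches to Mann-Whitney when data are non-normal, so that column is the relevant comparator for skewed data. With a Shapiro-Wilk trigger in either arm (an assumption, since 9.4 names no normality test), the rule picks Mann-Whitney in about 98% of trials at CV 0.7. Power is then 26% against 27% on logs for a 20 percent reduction, and about 85% against 87% for 40 percent. The gain is 1 to 3 points.

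**5. Does the log scale estimate the same thing?** A lognormal mean equals the geometric mean × √(1 + CV²). With control CV 0.7 and device CV 0.5 (assumed), a true ratio of means of 0.80 corresponds to a ratio of geometric means of 0.80 × √(1.49/1.25) = 0.87. The two ratios agree only when the log-scale spread is equal in both arms.

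**The case against.** The strongest reply has four parts.

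- **Sizing on a percentage and testing in mL is not a contradiction.** Twenty percent of an expected control mean is an absolute difference, and under randomisation the mean difference in mL is valid with open and laparoscopic cases pooled. This stands. A reader might infer that the planned tests are invalid, or that pooling biases them; the documents support neither.
- **The plan already guards against skewness.** This also stands. A reader might infer that analysing mL wastes substantial power. The large gaps appear only when the raw t-test is applied to heavily skewed data, which the plan's own rule would rarely do. The documents also say nothing about how skewed blood loss is.
- **A log analysis changes the target.** Section 9.3 does not mention geometric means, and if the device mainly prevents heavy bleeds, the geometric-mean ratio understates the fall in mean volume (0.87 against 0.80 in step 5). This stands as a reason to show both measures. The log scale is one sound way to obtain a ratio, not the only valid one; a ratio of arithmetic means with its CI would also answer 9.3.
- **A confidence interval is promised for the multivariate results.** True, but it is attached to an odds ratio. It would be wrong to say that every planned analysis is either in raw mL or a rank test, since logistic regression is also listed. Dichotomising blood loss would still not estimate a 20 percent reduction.

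The descriptive and feasibility labels do not remove the point. They make an estimate with its interval more useful than a P value.

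**Conclusion.** The point holds as a gap in the effect measure and its reporting. The trial is sized on a ratio of 0.80, and 9.4 commits to no estimate of that ratio, or of any percent reduction, with a confidence interval. The odds-ratio sentence is a plain mismatch with a linear model in mL, and this needs no assumption to see.

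What would go unreported is substantial: about 0.63 to 1.02 at CV 0.5, or 0.58 to 1.11 at CV 0.7, around an observed 0.80. These figures assume lognormal data, a common CV and all 60 patients analysed. The CVs are assumptions; the gap itself does not depend on them.

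The documents do not use the word relative. It is the only workable reading of a percentage difference in a volume when no mL figure is given.

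**What to change.** In 9.4:

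1. Keep the planned test. Name as the primary effect estimate the Thunderbeat / conventional ratio of estimated blood loss with its 95% CI, read against 0.80.
2. Obtain it from a linear model on the natural log of blood loss with arm as a term, back-transformed to a ratio of geometric means. Run the blood-loss regression on the same scale.
3. Show arithmetic means by arm, and their ratio or their difference in mL, alongside. Say that the two ratios can differ if the spread differs between arms.
4. State in advance how any recorded zero loss is handled, since it has no logarithm.
5. Limit the odds-ratio sentence to the binary outcomes, and state that linear models are reported as differences or ratios with 95% CIs.

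The cost is a few sentences, with no new data and no extra patients. The small downside is that a ratio of geometric means is less familiar to surgeons than a difference in mL; item 3 covers this.

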5.5 Duration of Follow-Up

Patients will be followed for 90 days following their surgical procedure. Postoperative complications and adverse events will be closely monitored. Patients will be followed until resolution or stabilization of the adverse event. Please see Appendix B for Study Visit Schedule.

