6.0 ADVERSE EVENT REPORTING

6.1 Adverse Events

Definition: any unfavorable medical occurrence in a human subject including any abnormal sign, symptom, or disease.

Attribution (relatedness), Expectedness, and Seriousness: the definitions for the terms listed that should be used are those provided by the Department of Health and Human Services' Office for Human Research Protections (OHRP). A copy of this guidance can be found on OHRP's website:<http://www.hhs.gov/ohrp/policy/advevtguid.html>

The surgeon will discuss the expected risks of the surgery with the participant and participant and a separate surgical consent for the surgery acknowledging the risks. Expected risks of the surgery are listed below.

- **Perioperative complications:**
iatrogenic injury, convert from laparoscopic approach to open procedure, use of other

hemostatic devices or therapies, blood transfusion

- **Postoperative complications:**

Secondary bleeding/hematoma, delirium, failure to thrive, urinary retention, surgical site infection, urinary tract infection, C-diff, colitis, ileus, delayed gastric emptying, fistula, anemia, pneumonia, intraabdominal abscess, atrial dysrhythmia, myocardial infarction, cellulitis, deep vein thrombosis/pulmonary embolism, anastomotic leakage, re-intervention (operational), blood transfusion, sepsis, death.

The above are complications of the surgical procedure and may be experienced by all patients on whom a Whipple procedure is performed. Surgical complications are routinely identified and documented during the data abstraction process for the American College of Surgeons National Surgical Quality Improvement Program® (NSQIP). NSQIP has very detailed and specific definitions used to assess these postoperative morbidities. For the purposes of this study, the NSQIP definitions for the surgical complications will be utilized.

Surgical complications will not be considered adverse events associated with the study, unless unanticipated and possibly related to the use of the Thunderbeat device. If an adverse event is reported, details related to the event will be obtained from medical record review and direct communication with the PI for severity and relatedness assessment. The adverse event will then be recorded as part of the research and reported as necessary. If it is determined by the PI that the event is anticipated from surgery and not related to the device, it will not be reported as an adverse event as part of this study.

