APPENDIX B: STUDY VISIT SCHEDULE

	Baseline	Intervention	Follow-Up		
	Screening ²	Day of Surgery	Hospital Discharge	30 Day Post-Op Visit ³	90 Day Status ⁵
Past medical history ¹	X				
Informed consent	X				
Physical exam ⁴	X				
Operating time from skin incision to closure (mins)		X			
Anesthesia time (mins)		X			
Intraoperative estimated blood loss (cc)		X			
Administration of blood products		X	X		
Peri and postoperative complications		X	X	X	X
Hospital length of stay			X		
Mortality			X	X	X

¹Study-relevant past medical and surgical history

²Screening procedures to be completed within 60 days of surgery.

³To be performed 30 days from day of surgery \pm 14 days.

⁴Baseline height, weight, gender, karnofsky performance status, medications from pre-surgical physical examination

⁵Medical records (inpatient and outpatient) will be reviewed by a study team member for additional postoperative complications. No direct contact or clinic visit required.

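### Hospital length of stay has no rule for in-hospital death or readmission; at face value an early death counts as a short stay and readmission days are lost

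*Combined protocol and SAP*

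**What the plan says.** Section 9.1 gives length of stay secondary status: "The secondary objectives are intraoperative and postoperative morbidity, hospital length of stay and operative time". It is not in the list of secondary endpoints later in that section, nor in section 2.2.

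Section 9.4 treats it in days. The two-group comparison is a t-test for continuous variables, and Mann-Whitney "tests will be utilized for non-normally distributed variables". The multivariate sentence includes "hospital length of stay (days) will be performed using binary logistic regression and linear regression models", and the next sentence adds: "The results of multivariate analyses will be expressed as odds ratios with corresponding 95% confidence intervals".

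In the Appendix B schedule, the row "Hospital length of stay" has one mark, which by position falls under hospital discharge. There is none at 30 or 90 days. Mortality is marked at discharge, 30 days and 90 days, and complications are marked from the day of surgery through day 90.

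Death is foreseen. Section 6.1 ends its list of expected postoperative complications with "blood transfusion, sepsis, death", and section 9.1 has "Hospital mortality" as an endpoint. Section 5.5 states: "Patients will be followed for 90 days following their surgical procedure". No section gives a start or stop for length of stay, says whether it means the index stay or all hospital days, or says what happens to it when a patient dies. Readmission is not mentioned.

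**The concern.** Fewer days is read as better. A patient who dies in hospital on day 3 has a recorded stay of 3 days, shorter than a typical survivor's. In a rank test that patient takes one of the lowest, most favourable ranks. A patient discharged on day 7 and readmitted for 10 days with an abscess contributes 7 days, the same as one who goes home on day 7 and stays there.

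The complications on which the two techniques might differ, such as secondary bleeding, fistula, abscess and leak, are followed to day 90, and some will appear after discharge. Section 9.1 also counts costs to 90 days, so length of stay and cost would cover different periods. Section 5.2 says surgeons cannot be blinded. A scoring rule left open until deaths and readmissions are known by arm is avoidable discretion.

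**Working it through.** **Plan's own figure.** There is none for length of stay. The sample-size statement in section 9.3 concerns blood loss; only its 30 patients per arm is used here. Mean stay, death rate and readmission rate below are all assumptions.

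**1. Effect of an early death on an arm mean.** If the other patients in an arm of 30 average m days and d patients die on day t, the mean shifts by −d(m − t)/30.
- m = 12, t = 3, d = 1: −(12 − 3)/30 = −0.3 day. With d = 2: −0.6 day.
- Smallest shift for one death over m = 8 to 14 and t = 1 to 5: −(8 − 5)/30 = −0.10 day. Largest: −(14 − 1)/30 = −0.43 day.
- Three deaths over the same range: −0.30 to −1.30 days.

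Each shift is in the favourable direction. A death later than the arm's mean stay shifts it the other way.

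**2. Scale against sampling error.** With an assumed SD of 6 days, the standard error of the difference between arms is 6 × √(2/30) = 1.55 days. One day-3 death moves the difference by 0.3/1.55, about one fifth of a standard error.

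**3. Chance that the case arises.** The probability of at least one death among 60 is 1 − (1 − p)^60.

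| Assumed death rate p | P(at least one death in 60) |
|---|---|
| 1% | 45% |
| 2% | 70% |
| 3% | 84% |
| 5% | 95% |

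**4. Direction when deaths are unbalanced.** A simulation used 20,000 trials, 30 per arm, the same stay distribution in both arms (log-normal, median 9 days, log-SD 0.45) and deaths on days 1 to 5.

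| Death rate, arm A vs arm B | Raw mean stay favours A | Mean rank, deaths ranked worst, favours A |
|---|---|---|
| 3% vs 3% | 50% | 50% |
| 7% vs 3% | 58% | 39% |
| 10% vs 3% | 65% | 32% |

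At 10% vs 3%, the raw mean difference averages −0.48 day in favour of the arm with more deaths.

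**5. Readmission days left out.** Days omitted per patient = readmission rate × days per readmission. With 10% to 30% readmitted for 4 to 10 days, this runs from 0.1 × 4 = 0.4 to 0.3 × 10 = 3.0 days. This is an omission, not a difference between arms, and it cancels if readmission is balanced. If one arm had 20% and the other 10%, at 7 days each, the missed difference would be (0.2 − 0.1) × 7 = 0.7 day.

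**6. The same patients under days alive and out of hospital to day 90.** The day-3 death scores 0. The patient discharged on day 7 scores 90 − 7 = 83 if not readmitted, and 83 − 10 = 73 after a 10-day readmission.

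**The case against.** A reader might infer that the plan measures raw days to first discharge and so scores an early in-hospital death as the best result. The documents do not say that. They never specify first discharge and never state how a death is scored. A patient who dies could be set missing or excluded, and naming logistic regression with odds ratios leaves room for a dichotomised stay. Only a death before the usual discharge day looks favourable. The face-value reading is the natural one, but it is not written down.

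A reader might also infer that the trial would miss the harms. It would not. Mortality is collected at every follow-up point, the relevant complications are endpoints in their own right through 90 days, section 9.4 reports complication incidences with confidence intervals, and later hospital use can enter the 90-day cost. An arm with more deaths or abscesses would show it beside length of stay.

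The weight is also limited. The outcome is secondary, section 9.4 calls the analysis descriptive, and one death shifts a mean by a fraction of its standard error. Index length of stay is a legitimate measure of resource use, so replacing it outright would be a trade-off.

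All of this stands, and it limits the size of the point. It does not supply the missing rule: the plan foresees in-hospital death, and reporting deaths elsewhere does not say what the length-of-stay comparison does with them.

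**Conclusion.** The point holds as a gap with a cheap remedy. Length of stay is a secondary objective analysed in days and apparently recorded once at discharge, with no rule for in-hospital death or readmission. At face value, early deaths count as favourably short stays and readmission days within the 90-day follow-up are lost.

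The likely size is small: 0.3 day per day-3 death at an assumed 12-day mean, and 0.10 to 0.43 day over the wider range. It matters if deaths or readmissions differ between arms, because the raw comparison then leans towards the arm with more early deaths. The readmission figure of 0.4 to 3.0 days per patient should not be read as bias. All of these sizes rest on assumed rates and stays, and the timing of collection rests on the position of a single mark in the Appendix B table.

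**What to change.** - **Sections 9.1 and 9.4:** define length of stay as the index stay, in days from surgery to discharge alive, and add it to the secondary endpoint list.
- **Section 9.4:** compare arms by Mann-Whitney with in-hospital deaths ranked as the longest stay. If the linear or logistic model is kept, state how deaths enter it.
- **Section 9.4:** add days alive and out of hospital from surgery to day 90 as a supportive analysis, with days after death counted as zero and readmission days subtracted.
- **Appendix B and the RedCap follow-up form:** record all readmission and discharge dates at the existing day-90 review, which already covers inpatient records.

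The cost is some plan wording and a few date fields, which must be repeatable because a patient can be readmitted more than once. The supportive measure is less familiar to surgeons than length of stay. Because day 90 is a record review without patient contact, stays at other hospitals may be missed and would then count as days at home; the report should say so.
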